4.2.1. Enrollment Visit

Women who agree to study participation will be consented for 9 months of follow-up. Women who are confirmed HIV- and not pregnant will be randomized to participate in one of two basic strategies for adherence support:

- Standard of care adherence counseling sessions and WhatsApp group participation
- Standard of care adherence counseling sessions and weekly two-way SMS communications

Randomization will be conducted with a ratio of 1:1 between the two study arms. Envelopes will be used to assign primary randomization.

Locator information will be collected and mobile phone numbers will be validated and texting and WhatsApp capacity assessed. Demographic and behavioral data will be collected, including information about HIV and pregnancy risk perception, depressive symptoms, trauma, stigma, HIV prevention, self-efficacy, self-esteem, sexual relationship power, transactional sex, intimate partner violence, alcohol and drug use, sexual behavior (number of partners, partner's HIV status, vaginal and anal sex with partners), and PrEP interest and readiness.

Clinical evaluations and procedures will include a contraception assessment, counseling and provision if desired, HIV pre and post-test counseling, risk reduction counseling and condom provision. Medical history including assessment for acute HIV and STI symptoms and concomitant medications will be conducted and a symptom-directed physical exam will be performed if indicated. Women who have symptoms potentially consistent with acute HIV infection (fever, rash, pharyngitis) will have enrollment deferred for at least 2 weeks at which time repeat serologic testing will be performed (and if positive will result in study exclusion). STI treatment will be administered per local standard of care. Blood, urine, and a self-administered vaginal swab will be collected.

HIV testing will be conducted according to national algorithm. Testing will be conducted for pregnancy, Hepatitis B serology (HepBsAg), serum creatinine for creatinine clearance, and diagnostic STI testing for trichomonas, gonorrhea, chlamydia and syphilis. Plasma and DBS will be stored.

One bottle of PrEP will be dispensed and women will be counseled per South African national guidelines, including about the importance of high PrEP adherence to achieve high levels of HIV protection, frequency, type and timing of side effects with oral FTC/TDF, and strategies for confidential storage and anticipating barriers to adherence.

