6.4. Data Analysis

6.4.1. Primary Analyses

We will conduct primary analyses to assess the effect of the randomized interventions on drug concentrations at 9-months post-randomization by 1) comparing the first-stage intervention options on TFV-DP levels at the 9-month visit; 2) comparing the second-stage intervention options on TFV-DP levels at the 9-month visit among participants classified as “non-responders” to the initial intervention; and 3) comparing the four adaptive intervention strategies described in Table 1.

For the analyses of first-stage intervention options, logistic regression will be used to assess effect of the each primary randomized intervention on 9-month adherence by comparing TFV-DP levels in Groups 1-3 versus Groups 4-6 shown in Figure 1B on page 10. For the analyses of second-stage intervention options among non-responders, logistic regression will also be used to assess the effect of the intensified adherence intervention (second randomization) within each arm of the first randomization, and in the absence of interaction, pooled across the first randomization (Groups 2 and 5 versus Groups 3 and 6). For analyses comparing the adaptive intervention approaches, each of the 4 overall strategies (2 initial x 2 intensification interventions in non-responders) will be ranked by their overall adherence response (Table 3), with inverse-probability weighting and standard errors taking into account that women who respond to their first-assigned treatment are consistent with *two* of strategies embedded within our SMART design and over-represented in our analysis datasets. Because of the high expected post-randomization drop-out before M1, we will adjust for confounders of PrEP continuation and adherence and M1 drop-out in the analysis.

Table 3. Combination of adherence intervention strategies in SMART design. [Note that under each of the four strategies embedded in our trial design, young women who are adhering (“responding”) will continue to receive their originally-assigned method of support (i.e., WhatsApp groups or weekly two-way SMS).]

Standard of care brief counseling and one-way SMS reminder messages with WhatsApp peer support, followed by quarterly drug level counseling for non-responders
Standard of care brief counseling and one-way SMS reminder messages with WhatsApp peer support, followed by monthly visits with problem-focused counseling for non-responders

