PrEP or study participation among participants who were randomized but did not return to a study visit between months 1-3, as data are available.

- 3) Primary analysis: We will conduct an intent-to-treat analysis using modified Poisson regression to assess the effect of the first-line randomized intervention on 9-month adherence by comparing TFV-DP levels (\leq / \geq 700 fmol/punch) across participants receiving two-way SMS versus participants enrolled in the WhatsApp intervention. This main effect can be interpreted as the difference between the two first-line intervention options. The effect of the intervention will be estimated as a relative risk (RR) from the regression model, with study arm assigned at first randomization as the only predictor and robust standard error estimates.

Sensitivity analyses: If overall loss to follow-up in the full sample is $>10\%$ by month 9 or if differential loss to follow-up between the two arms is $>10\%$, we will repeat the primary ITT analysis using inverse probability weights to adjust for the potential impact of missing data.

Modified ITT analyses: We will conduct a modified ITT analysis using the same procedures described above (primary analysis) but restricting to participants who returned for at least one study visit between months 1 and 3.

- Since this analysis breaks randomization, we will adjust for important prognostic variables (including demographics, sexual behavior factors, and HIV risk factors) to account for treatment imbalances.

Per-protocol analyses: We will also conduct a per-protocol analysis using the same procedures described above but restricting to participants who received full doses of the SMS and WhatsApp interventions as described above in the *Measures of intervention use* section and adjusting for the same prognostic variables as in the modified ITT analysis.

Subgroup analyses: We will perform subgroup analyses to obtain subgroup-specific estimates of the intervention. These estimates will be generated using the same model and analysis population as described in the primary analysis (above) but will also include subgroup indicator variable(s) and an interaction term between the subgroup indicator and study arm in the model. Subgroups will be defined as follows:

- Age ≤ 20 years versus >20 years

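### Primary Analysis 1 leaves out baseline covariates the SAP already treats as predictors of adherence, and protocol and SAP should be reconciled on whether the first-stage comparison is adjusted

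*SAP*

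**What the plan says.** SAP, Primary Analysis 1, item 3, specifies modified Poisson regression of month-9 adherence (TFV-DP around 700 fmol/punch) in all randomised women, "with study arm assigned at first randomization as the only predictor and robust standard error estimates". Covariates enter only the modified ITT analysis, where "we will adjust for important prognostic variables (including demographics, sexual behavior factors, and HIV risk factors) to account for treatment imbalances", and the per-protocol analysis, which uses the same variables. If overall or between-arm differential loss exceeds 10%, "we will repeat the primary ITT analysis using inverse probability weights to adjust for the potential impact of missing data".

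Protocol section 6.4.1 states that "logistic regression will be used to assess effect of the each primary randomized intervention on 9-month adherence" and names no covariates there. At the end of the same text it adds: "Because of the high expected post-randomization drop-out before M1", "we will adjust for confounders of PrEP continuation and adherence and M1 drop-out in the analysis".

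On what is available, protocol section 4.2.1 says of enrolment: "Demographic and behavioral data will be collected, including information about HIV and pregnancy risk perception, depressive symptoms, trauma, stigma", with self-efficacy, relationship power, partner violence and substance use also listed. SAP Secondary Analysis 2 enters variables of this kind, measured at baseline, in a model for month-9 adherence, and reports very little missing baseline data.

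**The concern.** Two things are at stake. First, someone who reads both documents cannot tell whether the headline first-stage relative risk should be adjusted. Primary Analysis 2 calls arm the predictor of interest, which leaves room for covariates; Primary Analysis 1 explicitly rules them out.

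Second, adjusting for prognostic baseline variables in a randomised comparison can keep the same marginal estimand, reduce its variance and correct for chance imbalance. The SAP holds the variables and plans to model the same outcome on them, but does not use them in the analysis where precision matters most. The trial may have little power to spare: unless month-9 adherence in the lower arm is quite low, 350 women give well under 80% power for the 12-point difference in the SAP.

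**Working it through.** **Inputs from the documents.** 1:1 allocation, 175 evaluable per arm and one-sided alpha 0.025 (protocol 6.3); about 350 women for a difference of about 12 points at month 9 (SAP, Sample size). The SAP gives no control rate, alpha or power. Neither document gives the prognostic strength of the covariates.

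**Assumptions.** Covariate strength is expressed as R², the share of outcome variance explained, scanned from 2% to 20%. Control rates are scanned too.

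**Formula for power.** Φ{[Δ − 1.96·√(2p̄(1−p̄)/n)] / √([p0(1−p0)+p1(1−p1)]/n)}, with n per arm.

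**Step 1: the plan's own figures.** For 60% vs 40% at n = 175: [0.20 − 1.96 × 0.0535]/0.0524 = 1.82, so power is 96.6% (protocol: 96%). For 65% vs 40% the result is 99.8% (protocol: 99%). For 55% vs 40% it is 80.5% against a stated 84%. That row does not reproduce, but nothing below depends on it.

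**Step 2: unadjusted power for 12 points at month 9.** At 14% vs 26% it is about 80%. At 40% vs 52%: [0.12 − 1.96 × 0.0533]/0.0529 = 0.29, so power is 61.6%. The 40% is the protocol's month-2 planning rate, borrowed here only as an illustration.

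**Step 3: effect of adjustment.** Variance is multiplied by (1 − R²), which is the same as replacing n by n/(1 − R²).

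| R² | SE ratio √(1−R²) | Equivalent N, 350/(1−R²) | Power, 12% vs 24% | Power, 44% vs 56% |
|---|---|---|---|---|
| 0 | 1.000 | 350 | 83.5% | 61.3% |
| 2% | 0.990 | 357 | 84.2% | 62.2% |
| 5% | 0.975 | 368 | 85.3% | 63.5% |
| 10% | 0.949 | 389 | 87.2% | 65.9% |
| 15% | 0.922 | 412 | 89.0% | 68.4% |
| 20% | 0.894 | 438 | 90.7% | 71.0% |

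**Step 4: check by simulation.** With 350 women, three covariates and 1,500 trials per setting, adjusted modified Poisson gave these SE ratios:
- 12% control rate: 0.985 at R² 2.7%, 0.933 at 14%
- 40% control rate: 0.975 at R² 5.4%, 0.945 at 12%, 0.907 at 22%

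The formula is slightly optimistic for strong covariates: √(1 − 0.218) = 0.884 against 0.907.

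For the estimator recommended below (relative risk standardised from a logistic model, one real and four noise covariates):
- Variance of the log relative risk fell by about 2-15% at 33% vs 45%, with power going from 62-63% to 66-72%.
- Variance fell by about 2-10% at 14% vs 26%, with power going from 79-80% to 80-84%.
- The mean relative risk was unchanged and type I error was about 4-6%.
- With covariates of no prognostic value, variance rose by 1-2%. That is 350/1.01 = 347 to 350/1.02 = 343, the equivalent of 3 to 7 women.

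Simulated power at around 63% has a Monte Carlo error of √(0.63 × 0.37/1500) = 1.2 points with 1,500 runs. By formula, a 15% variance cut is worth 68.4 − 61.3 = 7 points at the higher control rate, and about 10 points needs R² near 20%. Ten points is therefore the outer edge.

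**Step 5: expected loss.** The protocol plans up to 500 randomised for about 350 analysed: 150/500 = 30%. On that expectation the SAP's 10% trigger for weighting would be met.

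**The case against.** The strongest reply is that nothing here is an error. With complete outcomes, an arm-only model with robust standard errors gives a valid marginal relative risk. The SAP follows a coherent rule: no covariates where randomisation is intact, covariates where it has been broken. That stands.

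A reader might infer that the SAP flatly contradicts the protocol on the main analysis. The documents do not support so strong a reading. The protocol's stated reason is drop-out before month 1, so its concern is bias, not precision. It names no covariates, and the sentence follows the text on the four adaptive strategies, so its reach to the first-stage comparison is unclear. The protocol's analysis sample is women who return at month 1. The nearest SAP counterpart is the modified ITT, which is adjusted, and the weighted analysis also addresses loss. Still, both are non-primary for this comparison, so the status of the headline estimate remains unsettled between the documents.

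It is also fair to say that strong covariates cannot be counted on. Reported PrEP use in the last 6 months is an exclusion, so there is no informative baseline drug level, and listing variables in Secondary Analysis 2 makes them candidate predictors, not proven ones. This limits the likely gain. It does not remove the case for adjusting, because the loss if they fail is only 1-2% of variance.

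**Conclusion.** The point holds as an efficiency and reconciliation matter. The two documents differ in wording on adjustment, and the primary model forgoes precision that could be had at almost no cost. With 350 evaluable women the variance of the log relative risk would fall by about 2-15% and power would rise by about 1-10 points. The smaller gains go with weak covariates or low control rates. These ranges rest on assumed R² and control rates, because the documents give neither.

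Two further inferences should be resisted. The unadjusted result is not biased merely because it is unadjusted; bias could arise from missing month-9 outcomes, which is a separate matter. And adjusting for predictors of adherence does not by itself deal with drop-out, so it does not replace the weighted analysis.

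**What to change.** 1. State in both documents whether the primary first-stage comparison is adjusted, and whether the protocol's sentence on month-1 drop-out applies to it or is met by the modified ITT and weighted analyses.
2. Pre-name four to six enrolment covariates from the Secondary Analysis 2 baseline tool, for example age, education, depression, PrEP self-efficacy, perceived HIV risk and partner violence. Fix the list and the coding before month-9 drug levels are examined by arm.
3. Make primary the marginal relative risk standardised from a logistic model containing arm and these covariates, with a robust standard error. This targets the marginal relative risk without assuming a constant effect across covariate levels.
4. Keep the arm-only modified Poisson relative risk as a sensitivity analysis.
5. Retain the inverse-probability-weighted analysis for missing month-9 outcomes.

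The cost is a paragraph in the SAP, a clarifying sentence in the protocol and a few lines of code. No new data are needed, and few women should be lost to missing covariates, given the SAP's own statement on baseline completeness.

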6.3. Accrual, Follow-up, and Sample Size

For the SMART trial design, the goal is to enroll and randomize up to 500 women in order to achieve an analysis sample size of approximately 350 women who return for their one-month study visit and will want to continue PrEP for a further 9 months: 175 per arm randomized into the first intervention at enrollment, continuing past their 1-month study visit and evaluable at 9 months. Up to 500 women who initiate PrEP will be enrolled over a period of approximately 18 months. 350 evaluable women

would have 96% power for the initial randomization to detect an increase from 40% response at 2 months to SOC + two-way SMS to 60% with the SOC + WhatsApp groups. Among the estimated 70-105 non-responders in each initial group, we have 79-96% power in each group of non-responders to detect a 30% difference in adherence at 9 months between women randomized to monthly counseling or drug level feedback. Pooling across the initial randomization, with 149-166 women we would have ~80% power to detect ~ 15-20% difference (Table 2).

Table 2: Power to assess differences in adherence by intervention strategies in each of the first and second stages using a one-sided $\alpha = 0.025$.

First Randomization			Second randomization (Pooled across first randomization)			
% Adherent				% Adherent		
WhatsApp + SOC N = 175	SMS + SOC N = 175	Power	Non-responders Total N	Monthly visits	Drug Level Counseling	Power
65%	40%	99%	166	40%	25%	84%
				50%	30%	89%
60%	40%	96%	175	40%	25%	86%
				50%	30%	91%
55%	40%	84%	184	40%	25%	88%
				50%	30%	91%

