At month 3, women who have TFV-DP <500 fmol/punch (based on a blood sample collected at month 2) or who miss PrEP refills at the month 1 or 2 visits will undergo a secondary 1:1 randomization to either continue monthly follow-up visits with problem-focused counseling until month 8 or attend quarterly visits with drug level feedback counseling at months 3 and 6. Women will also continue to receive the adherence support from their original randomization (i.e., WhatsApp groups or weekly two-way SMS).

Women who have TFV-DP ≥ 500 fmol/punch at month 3 (based on a blood sample collected at month 2) will continue to receive the adherence support in their original randomization (SOC adherence counseling, one-way SMS reminder messages, and either WhatsApp groups or weekly two-way SMS) with quarterly visits. **Table 1** depicts the four embedded dynamic treatment strategies and decision rules for determining non-adherence and re-randomizing women at their month 3 visit:

Table 1. Embedded dynamic treatment strategies and corresponding decision rules

Dynamic treatment strategy	Decision rule
Non-response definition: TFV-DP levels <500 fmol/punch or missed refills	
First, offer monthly SOC counseling and WhatsApp group intervention; then add drug level feedback with quarterly visits for non-responders and switch responders to quarterly SOC visits and continued WhatsApp groups	First-stage intervention option = {SOC + WhatsApp} IF evaluation = {non-response} THEN second-stage intervention option = {DLFB + first-stage intervention option + quarterly study visits}

	ELSE continue on first-stage intervention option + quarterly study visits
First, offer monthly SOC counseling and weekly two-way SMS intervention; then add drug level feedback with quarterly visits for non-responders and switch responders to quarterly SOC visits and continued weekly two-way SMS	
First-stage intervention option = {SOC + SMS}
 
IF evaluation = {non-response}
 
THEN second-stage intervention option = {DLFB + first-stage intervention option + quarterly study visits}
 
ELSE continue on first-stage intervention option + quarterly study visits

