- 2) Primary analysis: We will use modified Poisson regression to assess the effect of the randomized second-line intervention on 9-month adherence by comparing TFV-DP levels across participants receiving monthly counseling versus participants receiving drug-level feedback, separately for (1) non-responders to the first-line SMS intervention and (2) non-responders to the first-line WhatsApp intervention. The effect of the randomized intervention will be estimated as a relative risk (RR) from the regression models, with study arm assigned at second randomization as the predictor of interest and robust standard error estimates.

Sensitivity analysis: If overall loss to follow-up in the full sample is $> 10\%$ by month 9 or if differential loss to follow-up between the two arms is $> 10\%$, we will repeat the primary analysis using inverse probability weights to adjust for the potential impact of censoring due to missing data.

Subgroup analysis: Subgroup-specific estimates of the intervention will be generated using the same models and analysis population as described in the primary analysis (above) but will also include subgroup indicator variable(s) and an interaction term between the subgroup indicator and second-line study arm in the model. Subgroups will be defined as follows:

- Age ≤ 20 years versus > 20 years
- 3) Secondary analyses:
 - We will also assess the effect of the intervention on the continuous PrEP adherence outcome using linear regression models to assess the difference in mean TFV-DP levels between those in the monthly problem-focused counseling group and those in the drug-level feedback group at month 9. If less than 40% of the sample has drug undetectable drug levels, we will assign those with undetectable drug levels a numeric drug level equal to half the limit of detection. If more than 40% of the sample has undetectable drug levels, we will reassess the value of this analysis.

- We will also consider evaluating the effect of second-line treatment stratified by reason for non-response; however, if the number of participants available for these stratified analyses is insufficient, we will not pursue these analyses.

Primary Analysis 3: Among the embedded dynamic treatment strategies, identify the optimal adherence support strategy in terms of PrEP adherence at the nine-month study visit, where additional adherence support is provided to those who have low adherence after the first two months of PrEP use.

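### SAP Primary Analysis 2 lacks the pooled second-stage comparison that the protocol plans and that Table 2's second-stage power describes

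*SAP*

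**What the plan says.** Protocol 6.4.1 analyses the second-line options by logistic regression, first separately by initial arm. It then adds a further comparison, made "in the absence of interaction, pooled across the first randomization (Groups 2 and 5 versus Groups 3 and 6"). The second-stage half of Table 2 in protocol 6.3 is headed "Second randomization (Pooled across first randomization"), and it gives power for 40% versus 25% and for 50% versus 30% adherent. The text above the table sizes the within-arm tests separately: "Among the estimated 70-105 non-responders in each initial group, we have 79-96% power in each group of non-responders to detect a 30% difference in" month-9 adherence.

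In SAP Primary Analysis 2 the analysis population is all re-randomized women, but the primary model for the binary outcome is fitted "by comparing TFV-DP levels across participants receiving monthly counseling versus participants receiving drug-level feedback, separately for (1) non-responders to the first-line SMS intervention" and, second, for WhatsApp non-responders. The SAP has no pooled model for this outcome, no interaction assessment between second-line and first-line arm, no second-stage power and no reason for leaving pooling out. Its only sizing statement concerns a difference of about 12 points between the first-line arms.

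**The concern.** Monthly counselling versus drug-level feedback is one of the SAP's three primary questions. Splitting the re-randomized women by first-line arm answers it twice in small groups, when the same randomized data also support a single, more precise answer.

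Even if the true effect is the same in both groups, one test may well be significant and the other not. That could be misread as evidence that the better second-line option depends on the first-line arm. The SAP gives no rule for reading two such results together. If the pooled estimate is added only after the results are known, it will look post hoc, although the protocol planned it.

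**Working it through.** **Inputs**
- Significance level, protocol Table 2: "using a one-sided $\alpha = 0.025", so z = 1.96. The SAP states no level.
- Allocation, SAP Study Design: women "will undergo a secondary 1:1 randomization to either continue monthly follow-up visits" or move to drug-level feedback.
- Stratum sizes, protocol 6.3: 70 to 105 non-responders per first-line arm. With 175 per arm, 60% response to WhatsApp leaves 70 and 40% response to SMS leaves 105. Their sum, 175, is the total in the middle row of Table 2. Per second-line arm this is 35, 52.5 and, pooled, 87.5.
- Assumption: every non-responder is evaluable at month 9.

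**Formulas**
- SE = sqrt{[p1(1−p1) + p2(1−p2)]/n}, with n per second-line arm
- Power = Φ(|p1−p2|/SE − 1.96)
- Half-width = 1.96 × SE

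**The plan's own figures**
- Table 2, first row ("65% 40% 99% 166 40% 25% 84"%): a total of 166 gives n = 83. SE = sqrt(0.4275/83) = 0.0718, and power = Φ(0.15/0.0718 − 1.96) = 55%. The stated 84% appears only if 166 is taken as the number per arm: SE = 0.0507, power 84%.
- At totals of 166/175/184, 40% versus 25% gives 55/57/60%, or 54/56/59% with the pooled-variance formula. The table states 84/86/88%.
- At the same totals, 50% versus 30% gives 77/79/81%, or 75/78/80%. The table states 89/91/91%. Taking the totals as per-arm numbers gives 96–98%, so these entries match neither reading.
- The text of 6.3 says that "with 149-166 women we would have ~80% power to detect ~ 15-20% difference (Table 2"). Table 2 uses 166–184 women. At 149, pooled-variance power is about 50% for 40% versus 25% and 71% for 50% versus 30%.
- The 79–96% within-arm power for 30 points is attainable. With lower rates of 10–20%, the pooled-variance formula gives 76–84% at 70 women and 91–96% at 105. The protocol does not state the rates.

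**Within arm versus pooled, for Table 2's effects**

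| | 70 women (n = 35) | 105 women (n = 52.5) | Pooled 175 (n = 87.5) |
|---|---|---|---|
| 40% v 25%: SE | 0.1105 | 0.0902 | 0.0699 |
| 40% v 25%: power | 27% | 38% | 57% |
| 40% v 25%: half-width | 22 points | 18 points | 14 points |
| 50% v 30%: SE | 0.1146 | 0.0936 | 0.0725 |
| 50% v 30%: power | 41% | 57% | 79% |

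Pooled-variance power is 1 to 2 points lower throughout. For 80% power within one arm, with a lower rate of 25–30%, the difference must be about 32–33 points at 70 women and 26–27 points at 105.

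**Joint result of two independent tests when the true effect is equal**
- 40% versus 25%: both significant 0.273 × 0.383 = 10%; neither 0.727 × 0.617 = 45%; discordant 45%.
- 50% versus 30%: both significant 0.415 × 0.570 = 24%; neither 0.585 × 0.430 = 25%; discordant 51%.

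**Strength of the interaction test (risk-difference scale, 40% versus 25%)**
The SE of the difference between the two stratum effects is sqrt(0.1105² + 0.0902²) = 0.143. The stratum effects must differ by 1.96 × 0.143 = 28 points to reach significance, and by (1.96 + 0.84) × 0.143 = 40 points for 80% power.

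**The case against.** The SAP states the stratified question consistently as a primary objective. A SMART looks for good sequences, so a second-line effect that depends on the first-line arm is of real interest. The within-arm estimates are valid, and protocol 6.3 sizes that test. The protocol itself pools only conditionally. The chance that at least one within-arm test is significant is 55% or 75%, close to the pooled 57% or 79%. The sizes of 70 and 105 are one scenario, and missed refills also count as non-response, so the strata could be larger.

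Most of this stands, and it is why the within-arm estimates should stay. It does not supply the missing analysis. A rule that counts either test as success has a two-sided error rate of 1 − 0.95² = 9.8%, and one significant result of two is weaker evidence than one pooled result. The strata could also be smaller: Table 2's first row implies 166 − 105 = 61 WhatsApp non-responders, with power of 24% and 37%.

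The SAP's other analyses do not fill the gap:
- Primary Analysis 3 compares whole strategies, responders included, and its only contrast is a global test.
- The non-responder tool contains both arm variables but is a prediction model.
- The continuous secondary analysis does not say whether it is stratified, so it would go too far to say that no pooled estimate exists anywhere in the SAP.

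A reader might infer that the trial keeps only 27–57% power for the effects it was sized on. The documents do not support this, because 6.3 sizes the within-arm tests for 30 points. A reader might also infer that both tests will most likely fail; the chance is 45% or 25%. Nor can it be said that the SAP removed the pooled test. The SAP plans 12 months of follow-up and the protocol 9, and the order of the two texts is not established.

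**Conclusion.** The two documents disagree on a primary question, and the SAP lacks the more precise of the protocol's two second-stage analyses. For Table 2's effects, the within-arm tests have about 27–57% power and the pooled test 57–79%. Within-arm intervals are about 1.6 and 1.3 times as wide as the pooled one (22/14 and 18/14). With equal true effects, the two tests disagree about half the time (45–51%).

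These figures assume 70 and 105 non-responders, 1:1 allocation, a two-sided 5% level and no loss by month 9; losses would lower all of them.

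Two stronger conclusions are tempting but not supported. Pooling would not bring power to the 84–91% in Table 2, because that table does not reproduce at its own totals. And nothing requires the pooled estimate to replace the within-arm ones: that is a debatable trade-off, whereas adding it is a cheap gain.

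**What to change.** In SAP Primary Analysis 2:
- Add one modified Poisson model with robust standard errors on all re-randomized women, with second-line arm and first-line arm as predictors.
- Report the second-line by first-line interaction, and keep the two within-arm relative risks.
- Prespecify that the pooled estimate is reported whatever the interaction p-value. This goes further than protocol 6.4.1, which pools only in the absence of interaction, but the interaction test is too weak at this size to decide the matter. The protocol wording should be aligned.

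In protocol 6.3:
- Restate pooled power in Table 2 with the correct per-arm numbers: about 54–60% for 40% versus 25% and 75–81% for 50% versus 30%. For 80% power, about 304 and 186 non-responders in total would be needed.
- Reconcile the 149–166 in the text with the 166–184 in the table, and state the rates behind the 30-point claim.

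If analysis within arms alone is intended, the SAP should say why and state its power.

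The cost is a paragraph and one extra model. The small downside is that the pooled relative risk averages over the strata if the effects truly differ; the within-arm estimates remain on show for that reason.
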